A 16-week, open-label, multicenter, Phase 2 trial evaluated vadadustat in 94 subjects receiving chronic hemodialysis previously maintained on epoetin alfa and IV iron form the 3 months prior to Screening (Study AKB-6548-CI-0011 [CI-0011]). Subjects were assigned to one of three vadadustat dose cohorts: 300 mg daily, 450 mg daily, or 450 mg three times a week (TIW). Dosing was fixed for the first 8 weeks; for the subsequent 8 weeks dose was adjusted according to Hb response based upon a dose adjustment algorithm. Sixty-nine of the 94 subjects completed the study. The primary endpoint was the mean Hb concentration change from pre-treatment average (Screening Visit 1, Screening Visit 2, and Baseline Visit) to mid-study (Weeks 7 to 8) and end-of-study (Weeks 15 to 16) and was analyzed using observed Hb values (no imputation for missing data). No statistically significant mean change in Hb from pre-treatment average was observed for either of the two time points for any of the three treatment groups.

Among subjects randomized to an initial dose of 300 mg daily, 450 mg daily, or 450 mg TIW, 0% (0 of 30), 3% (1 of 33), and 19% (6 of 31) of subjects withdrew from the study due to worsening anemia, respectively. In a sensitivity analysis using last observation carried forward (LOCF) for the primary efficacy endpoint, no significant mean change in Hb from pre-treatment levels was observed in the 300 mg daily dosing group. At Weeks 15 to 16, modest, statistically significant mean decreases were observed in the 450 mg daily and 450 mg TIW dosing groups.

In a post-hoc univariate analysis of baseline characteristics, higher pre-baseline epoetin alfa dose was associated with a decrease in mean Hb at Weeks 7 to 8 and Weeks 15 to 16 in the dosing cohorts. Subjects who discontinued the study due to worsening anemia had a higher mean pre-baseline epoetin alfa dose compared with subjects who discontinued due to other reasons or subjects who completed the study.

Based on Phase 1 and Phase 2 study results, vadadustat appears to be a suitable candidate for continued development as a treatment for anemia in patients with CKD.

In the ongoing global Phase 3 and Japanese Phase 3 clinical studies, over 7000 subjects are planned to be treated with vadadustat or comparator.

This study will evaluate efficacy, safety and PK/PD with different vadadustat dosing strategies in hemodialysis subjects converting from epoetin alfa to further characterize the optimal vadadustat regimen.

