**Procedures** – Diagnostic and therapeutic non-invasive and invasive procedures, such as surgery, will not be reported as AEs. However, the medical condition for which the procedure was performed will be reported if it meets the definition of an AE. For example, an acute

appendicitis that begins during the AE reporting period will be reported as the AE and the resulting appendectomy noted under ‘Comments’.

Pre-planned therapeutic procedures not associated with a new medical condition or worsening pre-existing condition will not be reported as AEs.

**Pre-existing Conditions** – In this study, a pre-existing condition (i.e., a disorder present before the AE reporting period started and noted on the pretreatment medical history/physical examination form) will not be reported as an AE unless the condition worsens or episodes increase in frequency during the AE reporting period.

**Abnormal Test Findings** – All laboratory test results will be reviewed by the Investigator. The Investigator will utilize his/her judgment in determining if out-of-range laboratory values are clinically significant and will denote this using the abbreviation “CS” on the laboratory report for source documentation. Laboratory tests that are labeled as clinically significant will be reported as AEs, either separately or as part of a description of a symptomatic AE. If there are significant changes in a laboratory report from a previous visit that are determined to be clinically significant, these will also be reported as AEs. Any abnormal laboratory value which requires treatment or further diagnostic testing and/or results in discontinuation from study will be reported as an AE. An expected laboratory abnormality from a condition that is part of the medical history is not considered clinically significant for the purposes of the study unless it represents a worsening of the condition.

**Abnormalities in ALT, AST, and Total Bilirubin** – Abnormalities in ALT, AST, and total bilirubin will be reported to the Sponsor’s Medical Monitor or Contract Research Organization (CRO) designee within 24 hours of awareness as an SAE with ‘other medically important event’ criteria selected, if the following conditions are met:

- New elevation in ALT or AST >3 times ULN, with or without an elevation of total serum bilirubin >2 times ULN, AND
- No other reason was identified that explains the increased ALT/AST with or without an increased bilirubin (e.g., viral hepatitis, acute liver disease).

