If new elevations in ALT or AST >3 times ULN, with or without an elevation of total serum bilirubin >2 times ULN are identified, the following steps are to be taken:

- Temporary discontinuation of study drug;
- Repeat testing of ALT, AST, ALP, and total bilirubin, to be completed within 48 to 72 hours to confirm the abnormalities and to determine trend;
- Study drug will not be resumed until monitoring indicates abnormalities have resolved or are stable.

**Worsening of Anemia** – In this study, it is possible that some subjects may experience a worsening of anemia. As the primary endpoint of this study assesses Hb response, worsening of anemia is captured as part of this efficacy parameter. Worsening of anemia will not be considered an AE unless the worsening of anemia is associated with a cause *other than* the subject’s CKD.

**Transplantation** – During this study, it is anticipated that subjects may receive a kidney transplant. These events will not be recorded as AEs. Subjects who discontinue study drug for

receipt of a kidney transplant will complete the EOT visit (Visit 14) assessments and will complete the Safety Follow-Up (Visit 15) 4 weeks after Visit 14 as described in [Section 7.6.3](#), Early Discontinuation from Study.

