### 10.1.2 SAEs

Each AE is to be classified by the Investigator as SERIOUS or NONSERIOUS. An AE that meets 1 or more of the following criteria/outcomes is classified as serious:

- Death
- Life-threatening (see paragraph below on life-threatening)
- In-patient hospitalization or prolongation of existing hospitalization (see paragraph below on hospitalization)
- Persistent or significant disability/incapacity (see paragraph below on disability)
- Congenital anomaly/birth defect
- Is considered a medically important event not meeting the above criteria, but which may jeopardize a subject, or may require medical or surgical intervention to prevent one of the criteria listed in this definition.

In addition to the above criteria for classifying AEs as serious, the following situation will also be classified as serious for purposes of this study:

- Malignancies – Newly diagnosed malignancies or a recurrence of a malignancy will be reported as an SAE with the seriousness criterion “medically important” if no other seriousness criteria are met. If a subject develops basal cell carcinoma of skin, squamous cell carcinoma of skin, or cervical carcinoma in situ during the study, or has worsening of these events from baseline, the Investigator will determine if the event is reported as an AE or SAE.

Serious also includes any other event that the Investigator or Sponsor judges to be serious. If there is any doubt whether the information constitutes an AE or SAE, the information is to be treated as an SAE.

**Life-threatening** – Any event in which the subject was at risk of death at the time of the event; ‘life-threatening’ does not refer to an event which hypothetically might have caused death if it were more severe. For example, drug-induced hepatitis that resolved without evidence of hepatic failure would not be considered life threatening, even though drug-induced hepatitis of a more severe nature can be fatal.

**Hospitalization** – Hospitalization is defined as an overnight admission with observation of a minimum of 24 hours. A hospitalization planned before the start of the study for a pre-existing condition that has not worsened during the AE reporting period does not constitute an SAE unless an untoward event occurs related to the procedure (e.g., elective hospitalization for a total knee replacement due to a preexisting condition of osteoarthritis of the knee that has not worsened during the course of the study).

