### **11.7 Safety Analyses**

Safety analyses will be descriptive in nature.

All AEs will be coded using MedDRA. Treatment-emergent and post-treatment AEs will be summarized by SOC and PT for each treatment group. AEs will also be summarized by their maximum severity.

Summaries will also be provided for the following types of AEs:

- SAEs
- Related AEs, as determined by the Investigator
- AEs leading to early discontinuation of study drug

All Hb related safety endpoints will be tabulated for each treatment groups.

Observed values of continuous and categorical parameters and changes from baseline for continuous parameters to each study visit will be summarized descriptively for vital signs and clinical laboratory results. Graphical displays of selected laboratory parameters will also be provided.

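### The AE exemption for worsening anemia due to CKD has no exception for serious events and conflicts with neighbouring reporting rules

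*Protocol*

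**What the plan says.** Protocol Section 10.1.1, under Worsening of Anemia, reads: "Worsening of anemia will not be considered an AE unless the worsening of anemia is associated with a cause" other than the subject's CKD. The reason given is that the primary endpoint assesses hemoglobin (Hb), so "worsening of anemia is captured as part of this efficacy parameter".

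Earlier in the same section, under Abnormal Test Findings, the rule is: "Any abnormal laboratory value which requires treatment or further diagnostic testing and/or results in discontinuation from study will be reported as an AE". Section 10.1.1 also counts laboratory abnormalities that need clinical intervention as AEs, and a pre-existing condition becomes reportable once it worsens. Section 10.3.4 offers investigators failure of efficacy, or worsening of the condition under treatment, as a possible cause of an AE.

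Section 10.1.2 introduces its list of criteria with "An AE that meets 1 or more of the following criteria/outcomes is classified as serious". One criterion is "In-patient hospitalization or prolongation of existing hospitalization". The section then adds: "Serious also includes any other event that the Investigator or Sponsor judges to be serious". Section 10.3.3 sets a 24-hour clock for SAEs. Section 11.7 plans summaries of AEs, SAEs, related AEs and "AEs leading to early discontinuation of study drug".

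**The concern.** Seriousness is a property of an AE. Once an event is declared not to be an AE, the listed seriousness criteria no longer apply to it. The exemption turns only on cause and says nothing about severity or outcome.

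Inadequate response to study drug is a foreseeable problem in a conversion study. Vadadustat subjects leave epoetin alfa, while under Section 8.4.4 control subjects resume roughly their previous weekly dose. Safety is part of the primary objective. At stake are prompt notice of serious anemia events to the medical monitor, complete SAE counts, and consistent reporting across about 40 sites.

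**Working it through.** The plan gives no figure to reproduce. The check sets the rules side by side for one case: a subject admitted to hospital with severe anemia attributed to CKD and transfused.

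| Rule | Section | Result for this case |
|---|---|---|
| Worsening of Anemia | 10.1.1 | Not an AE |
| Laboratory abnormality needing clinical intervention | 10.1.1 | AE |
| Abnormal Test Findings | 10.1.1 | AE, because the value needed treatment |
| Pre-existing Conditions | 10.1.1 | AE, because the condition worsened |
| List of possible causes | 10.3.4 | Presupposes that such an AE can exist |
| Listed seriousness criteria | 10.1.2 | Hospitalization qualifies, but only for something already an AE |
| Clause on any other event judged serious | 10.1.2 | SAE if the investigator or sponsor so judges |
| Rule for doubt between AE and SAE | 10.1.2 | Does not decide whether the event is an AE at all |

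No order of precedence is written. Two readings follow.

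1. The specific sentence overrides the general rules. The case then bypasses the listed criteria and becomes an SAE only by discretion.
2. The general rules stand beside it. Two sites can then report the same admission differently, each citing the protocol.

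Neither reading secures consistent SAE reporting.

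**Does failure of vadadustat count as CKD anemia?** The text does not say so outright, but its usage points that way. Exclusion criterion 1 removes other causes of anemia at entry. The Week 12 transition criteria in Section 8.4.5.2 contrast worsening due to CKD with surgery, bleeding and inadvertent administration.

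**Does the stated reason hold?** The primary endpoint is a mean Hb change to Weeks 10 to 12 (Section 5.3.1). It records neither an admission nor a threat to life. Under Section 11.2 the Full Analysis Population needs an Hb value in that window, and the per-protocol population drops subjects rescued before it. A subject who leaves earlier because of anemia is in neither, and remains only in the Randomized population, with Hb carried forward (Section 11.5).

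**How foreseeable is the event?** Section 4.2 gives the number in each arm of the earlier hemodialysis study who "withdrew from the study due to worsening anemia": 0/30, 1/33 and 6/31. Intervals are exact 95% limits.

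- All arms: (0 + 1 + 6)/(30 + 33 + 31) = 7/94 = 7.4% (3.0 to 14.7%)
- Daily arms pooled: (0 + 1)/(30 + 33) = 1/63 = 1.6% (0.04 to 8.5%)
- Arm started on three-times-weekly dosing: 6/31 = 19.4% (7.5 to 37.5%)
- Share of non-completers: 94 − 69 = 25; 7/25 = 28%

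Planned vadadustat subjects, from the allocation ratios in Section 8.4.1:

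- Low-dose stratum: 2 × (40 × 3/8) = 30
- High-dose stratum: 3 × (55 × 3/11) = 45
- Hyporesponder study: 30 × 1/2 = 15
- Total: 90

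If the daily rate carried over (an assumption), 90 × 1/63 = 1.4 withdrawals for anemia would be expected, with probability 1 − (62/63)^90 = 76% of at least one. At the overall rate the figure is 90 × 7/94 = 6.7, which already includes the three-times-weekly arm. These are withdrawals, not serious events. The documents do not give the serious fraction.

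**The case against.** A reader might infer that CKD anemia can never be an AE or SAE under this protocol, even if fatal. The documents do not support that. Section 10.1.2 lets the investigator or sponsor judge any other event serious. Section 10.3.3 requires all deaths to be investigated and reported. The exemption covers worsening of anemia only, so a distinct consequence such as a cardiac event remains reportable.

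A reader might also infer that the harm disappears from the results and that the safety comparison is biased toward vadadustat. That too goes further than the text:

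- Low Hb with a decline from baseline is a safety endpoint (Section 5.5), tabulated by treatment group (Section 11.7).
- ESA rescue and transfusion are secondary endpoints, with reasons on the case report form (Sections 5.3.2.1 and 8.4.9).
- Lack of efficacy is a discontinuation reason (Section 7.6.3), and reasons are summarized by group (Section 11.4).
- Hb is measured at least every two weeks, and the study team reviews open-label safety data regularly (Sections 6.3 and 10.6).
- The exemption applies to both arms, and hyporesponders were not well controlled on epoetin to begin with.

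Finally, a reader might multiply 6/31 by 90 and expect about 17 omitted withdrawals. That arm went straight from epoetin to a three-times-weekly dose fixed for eight weeks. Here nobody starts on that schedule. Only subjects who meet the Week 12 criteria switch, and they may return to daily dosing. Any such withdrawals would also appear in the disposition table.

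These points defeat the absolute claims but do not close the gap. The discretionary clause is not a rule. The Hb, rescue, transfusion and disposition records carry no seriousness classification and no 24-hour notice. A Main-study subject admitted with symptoms at Hb 8.2 g/dL would not meet the low-Hb endpoint. The preference in Section 10.1.1 for a diagnosis over its symptoms could also draw fatigue or dyspnea into the exempted diagnosis.

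**Conclusion.** The concern holds in limited form. The exemption lacks an exception for events that meet a seriousness criterion, and it conflicts with other rules in Sections 10.1.1 and 10.3.4 without stated precedence. A subject hospitalized or endangered by CKD anemia may be left out of SAE reporting and the AE tables, or be reported differently from site to site. The other routes cover this only in part.

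The size cannot be fixed. The earlier study shows that withdrawal for worsening anemia is foreseeable, but the number of serious cases is unknown, and no bias in the safety comparison can be quantified.

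The conclusion assumes that inadequate drug response is attributed to CKD, as the protocol's usage suggests. It rests on the version whose Section 10 is shown. The later version breaks off at the start of Section 9. Its contents list shows the same Section 10 headings, but its wording cannot be checked.

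**What to change.** Replace the exemption sentence in Section 10.1.1 with:

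> Worsening of anemia due to CKD is not reported as an AE unless it meets a seriousness criterion in Section 10.1.2, in which case it is reported as an SAE.

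Cross-refer the laboratory, abnormal-test and pre-existing-condition rules of Section 10.1.1, and the criteria in Section 10.1.2, to this sentence so that they agree. Check that Section 10 of the amended version carries the same change.

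Making discontinuation a separate AE trigger is optional, since lack of efficacy is already summarized under disposition.

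The cost is a one-sentence amendment, a note to sites and a few more SAE reports. The change concerns reporting only and leaves treatment rules untouched.

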### 10.1.2 SAEs

Each AE is to be classified by the Investigator as SERIOUS or NONSERIOUS. An AE that meets 1 or more of the following criteria/outcomes is classified as serious:

- Death
- Life-threatening (see paragraph below on life-threatening)
- In-patient hospitalization or prolongation of existing hospitalization (see paragraph below on hospitalization)
- Persistent or significant disability/incapacity (see paragraph below on disability)
- Congenital anomaly/birth defect
- Is considered a medically important event not meeting the above criteria, but which may jeopardize a subject, or may require medical or surgical intervention to prevent one of the criteria listed in this definition.

In addition to the above criteria for classifying AEs as serious, the following situation will also be classified as serious for purposes of this study:

- Malignancies – Newly diagnosed malignancies or a recurrence of a malignancy will be reported as an SAE with the seriousness criterion “medically important” if no other seriousness criteria are met. If a subject develops basal cell carcinoma of skin, squamous cell carcinoma of skin, or cervical carcinoma in situ during the study, or has worsening of these events from baseline, the Investigator will determine if the event is reported as an AE or SAE.

Serious also includes any other event that the Investigator or Sponsor judges to be serious. If there is any doubt whether the information constitutes an AE or SAE, the information is to be treated as an SAE.

**Life-threatening** – Any event in which the subject was at risk of death at the time of the event; ‘life-threatening’ does not refer to an event which hypothetically might have caused death if it were more severe. For example, drug-induced hepatitis that resolved without evidence of hepatic failure would not be considered life threatening, even though drug-induced hepatitis of a more severe nature can be fatal.

**Hospitalization** – Hospitalization is defined as an overnight admission with observation of a minimum of 24 hours. A hospitalization planned before the start of the study for a pre-existing condition that has not worsened during the AE reporting period does not constitute an SAE unless an untoward event occurs related to the procedure (e.g., elective hospitalization for a total knee replacement due to a preexisting condition of osteoarthritis of the knee that has not worsened during the course of the study).

**Disability** – Defined as a substantial disruption in a person’s ability to conduct normal life functions.

## **10.2 Eliciting AE Information**

The Investigator is to report all directly observed AEs and all AEs spontaneously reported by the study subject. In addition, each study subject will be questioned about AEs at each visit following the initiation of study drug.

## **10.3 Reporting**

Each AE is to be classified by the Investigator as SERIOUS or NONSERIOUS.

All AEs that occur in study subjects during the AE reporting period specified in this protocol will be reported, whether or not the event is considered related to study drug (vadadustat or epoetin alfa).

### **10.3.1 Reporting Period**

The AE reporting period for this study begins upon receiving the first dose of study drug (vadadustat or epoetin alfa) and ends at the final protocol-required visit.

In addition, any SAE that occurs subsequent to the AE reporting period that the Investigator assesses as related to the study drug will also be reported as an SAE.

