- 12-Lead Electrocardiogram (ECG): A standard 12-lead ECG will be performed at Baseline/Day 1, which may be obtained up to 3 days prior to Baseline/Day 1. The ECG will be obtained after the subject has been resting comfortably in a supine position for approximately 5 minutes and will be taken prior to vital sign assessments and blood draws when possible. All ECGs will be reviewed by the Investigator for the presence of rhythms of potential clinical concern. A record of the tracing(s) will be made and retained with other source documents.
- AE Assessments: Beginning with the first dose of study drug (vadadustat or epoetin alfa) at Baseline/Day 1 and through study end (Follow-Up Visit), the Investigator and study personnel will review each subject's laboratory and clinical evaluation findings and query the subject directly regarding AEs (see [Section 10](#), Adverse Events). Subjects must be followed for AEs until the final required protocol visit (study end date) or until all drug-related toxicities and SAEs have resolved (or are considered chronic/stable), whichever is later.
- Prior and Concomitant Medication Recording: All prior and concomitant medications (except those routinely administered as part of the hemodialysis procedures, such as heparin or saline flushes used for routine catheter maintenance, unless relevant for an AE or SAE) taken within 30 days prior to Baseline/Day 1 and through the final study visit will be recorded on the appropriate CRF.

Iron treatment regimen 30 days prior to Baseline/Day 1 and through the final study visit will be recorded on the appropriate CRF. In addition, to ensure adequate collection of prior ESA dosing history, a minimum of 8 weeks of ESA therapy prior to start of study drug will be recorded on the appropriate CRF page.

At each study visit, subjects will be asked whether they have started, changed or discontinued any medication since their previous study visit. This includes single use or as needed medication use. All medications and changes in dosage and frequency will be recorded on the appropriate CRF Page. Documentation for all medicinal products will include the medication name, indication, dose, dosing frequency and dates of administration.

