### 9.3.1 Screening Visits

Subjects will need to sign a full consent form prior to SV1 procedures. The consent form may be signed in advance of the SV1 procedures. The Screening Period starts at the time the informed consent is signed and will be a maximum of 28-days in duration. Two Screening visits (SV1 and SV2) must be performed within the Screening Period and prior to dosing (Baseline/Day 1).

The Investigator will arrange for sufficient time (a minimum 4 days) between SV1 and SV2 and between SV2 or last retest (if applicable) and Baseline/Day 1 to allow for all laboratory results to be available that are required to assess eligibility for the next study visit.

In addition, subjects will be required to stop epoetin alfa treatment for a minimum duration of 5 days before Baseline/Day 1 in the Main study and for a minimum of 2 days before Baseline/Day 1 in the ESA hyporesponder parallel study.

After obtaining informed consent, subjects will undergo a number of Screening activities.

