### 9.3.1.2 SV2

At SV2, the following activities/procedures will be performed:

- Review of eligibility criteria
- Review of acceptable methods of contraception
- SF-36 and PGI-S assessments
- Physical examination (including height)
- Demographics and medical history
- Vital signs including temperature, HR, BP, RR and SO2 (assessed in seated position after 5 minutes of rest and prior to blood draws), and dry weight
- Laboratory procedures:
  - Serum pregnancy test for females of childbearing potential (eligible subjects will be advised to use an adequate contraceptive method see [Section 9.2.2](#), Laboratory Evaluations for additional information). A FSH test will be performed at SV2 for post-menopausal females.
  - CBC (without differential)

Subjects must have 2 Hb values measured by the central laboratory during Screening as indicated below:

- Main study: 2 Hb values between 8.5 and 11.0 g/dL, inclusive
- ESA hyporesponder parallel study: 2 Hb values between 8.0 and 10.0 g/dL, inclusive

If the subject's Hb does not qualify after SV1, SV2, or retest Hb, the subject will be considered a screen failure

- Visit registration in IWRS
- Introduction to and instruction on the use of the eDiary
- Prior and current medication use
- Epoetin alfa dosing will stop for a minimum of 5 days in the Main study or 2 days in the ESA hyporesponder parallel study until Baseline/Day 1

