## **12 DATA HANDLING AND RECORD KEEPING**

### **12.1 CRFs/EDC**

This study will utilize an EDC system to manage data collection during this trial. The system is fully Code of Federal Regulations 21 part 11 compliant. An EDC system contains certain functionality including, but not limited to, a graphical user interface to help facilitate data entry, a data validation element to check user data, and a reporting function to assist with the review and analysis of data. CRFs available through this system are required and will be completed for each randomized subject.

Any form of data from the electronic system are the sole property of the Sponsor and will not be made available in any form to third parties, except for authorized representatives of the Sponsor or appropriate regulatory authorities, without written permission from the Sponsor.

The Investigator has ultimate responsibility for the accuracy, authenticity, and timely collection and reporting of all clinical, safety, and laboratory data entered in the EDC or any other data collection forms. The CRFs will be signed electronically by the Investigator to attest that the data contained on the CRFs is true.

In most cases, the source documents are contained in the subject's chart at the hospital or the physician's office. In these cases, data collected on the CRFs will match the data in those charts.

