Overview of Study Design	This is a Phase 2, randomized, open-label study to evaluate vadarustat for the treatment of anemia in hemodialysis subjects converting from epoetin alfa therapy.  For all subjects (Main and ESA hyporesponder parallel study), the study will include a Screening Period, a Treatment Period, and a Safety Follow-Up Period as described below. PK and PD sampling will be done throughout the study (see PK and PD Sampling sections for details).  The aim is to achieve and maintain Hb levels within the target range of 10.0 to 11.0 g/dL, inclusive, while targeting the middle of the range and minimizing excursions outside the target range.  Screening Period (up to 28 days; Day -28 to Baseline/Day 1)  For all subjects (Main and ESA hyporesponder parallel study) the Screening Period starts at the time the informed consent is signed and will be a maximum of 28 days in duration. Baseline/Day 1 will be performed within 28 days of the start of Screening. Subjects who meet all eligibility criteria will be randomized to a vadarustat treatment arm or an epoetin alfa treatment arm. Subjects will be required to stop epoetin alfa treatment for a minimum duration of 5 days before Baseline/Day 1 in the Main study and for a minimum of 2 days before Baseline/Day 1 in the ESA hyporesponder parallel

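### AE and SAE reporting starts at the first study dose, so serious events during the protocol-required epoetin stop before Day 1 have no expedited reporting route

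*Protocol*

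**What the plan says.** Start of collection. Section 10.3.1 reads: "The AE reporting period for this study begins upon receiving the first dose of study drug (vadadustat or epoetin alfa". Section 9.2.1 and Appendix A footnote [m] give the same start: "Beginning with the first dose of study drug (vadadustat or epoetin alfa) at Baseline/Day 1 and through study end (Follow-Up Visit". On questioning, section 10.2 says "each study subject will be questioned about AEs at each visit following the initiation of study drug". Section 10.1.1 defines an AE as an occurrence within the reporting period, and section 10.1.2 defines an SAE as an AE that meets a seriousness criterion. The 24-hour rule in 10.3.3 therefore inherits the same start. The one extension in 10.3.1 runs forward, to related SAEs after the period ends.

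The step before the first dose. Section 9.3.1 says "subjects will be required to stop epoetin alfa treatment for a minimum duration of 5 days before Baseline/Day 1 in the Main study", with a 2-day minimum in the hyporesponder study. The SV2 list in 9.3.1.2 repeats it: "Epoetin alfa dosing will stop for a minimum of 5 days in the Main study or 2 days in the ESA hyporesponder parallel study". Section 8.4.1 places the stop after SV2, once eligibility has been met.

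What happens to events in between. On Day 1 (9.3.2) the site reviews eligibility again and reviews history and medication for anything new since SV2. A condition already present "will not be reported as an AE unless the condition worsens or episodes increase in frequency during the AE reporting period" (10.1.1). Medical history is MedDRA-coded and tabulated (11.3). For screen failures, 9.1.3 asks for a log and a documented reason. On data capture, 12.1 says "CRFs available through this system are required and will be completed for each randomized subject".

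Versions. The file holds two texts of the protocol, and only one shows Section 10. The other adds a bilateral nephrectomy exclusion, a statin section and a contents entry for an amendment history, so it appears to be later. It keeps the stop (its synopsis: "Subjects will be required to stop epoetin alfa treatment for a minimum duration of 5 days before Baseline/Day 1 in the Main study"), but its text breaks off at the start of Section 9.

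**The concern.** Stopping epoetin before Day 1 is something the protocol imposes on consented subjects. It is not usual care continuing. The study is about converting from epoetin, and the stop is the first part of the conversion. AEs head the list of safety endpoints in section 5.5, yet the collection window opens only after this step is over.

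Two things are at stake. The first is oversight: a serious event that follows from the stop does not oblige the site to report within 24 hours. The second is description: such an event cannot appear in the AE tables as a harm of conversion. Events serious enough to exclude the subject are the least visible, because the subject is never randomized or dosed and so falls outside the Safety Population (section 11.2). The protocol's own list of possible causes in 10.3.4 includes a protocol-related procedure, but this procedure lies wholly outside the window.

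**Working it through.** The protocol gives no event rate for this interval, so the check is a cross-reading plus date arithmetic.

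**Following one event through the rules.** Take a serious event after epoetin has stopped and before the first dose.

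1. It falls before the start in 10.3.1, 9.2.1 and footnote [m]. It is therefore neither an AE nor an SAE, and 10.3.3 does not apply.
2. If the event does not exclude the subject, it is recorded on Day 1 as a new condition since SV2 (9.3.2). It is coded as history (11.3) and becomes reportable only if it worsens or recurs more often after dosing (10.1.1).
3. If the event meets an exclusion in 7.3, the subject becomes a screen failure. Transfusion, active bleeding, acute coronary syndrome, heart-failure hospitalization, stroke and deep vein thrombosis or pulmonary embolism all do so. The visible text then requires only the log entry and reason (9.1.3).

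**Minimum time outside collection, randomized subjects.** Inputs: about 95 Main and 30 hyporesponder subjects (11.1); minimum stops of 5 and 2 days (9.3.1).

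- Main: 95 × 5 = 475 subject-days.
- Hyporesponder: 30 × 2 = 60 subject-days.
- Total: 475 + 60 = 535 subject-days, or 535 / 365.25 ≈ 1.5 subject-years.

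**Time inside collection.** Appendix A runs from Day 1 to Day 169, so 168 days per subject if all complete: (95 + 30) × 168 = 21,000 subject-days. The ratio is 535 / 21,000 ≈ 2.5%. Subjects taken off epoetin and never randomized would add to the 535; the protocol gives no count of them.

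**Longest gap.** No maximum is stated apart from the 28-day Screening Period. Assume SV1 falls on the day of consent and SV2 comes 4 days later, the minimum in 9.3.1.

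- Epoetin stopped at SV2 (9.3.1.2): 28 − 4 = 24 days.
- Epoetin stopped once SV2 results confirm eligibility (8.4.1), assuming 4 days for results: 28 − 4 − 4 = 20 days.

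**Main versus hyporesponder.** Subjects dialyze three times a week, and section 8.4.7 describes a long gap with two non-dialysis days, so sessions are 2 or 3 days apart. A 2-day stop fits within an ordinary interval. If epoetin was being given at each session, a 5-day stop skips at least one dose. The point therefore rests mainly on the Main study.

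**The case against.** The strongest reply is that this is a consistent choice of start point. Sections 9.2.1, 10.2, 10.3.1 and footnote [m] agree, no protocol rule is broken, and the stop is short. Much of that stands, and it rules out several stronger readings.

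- **That the comparison is biased.** The documents do not support this. Randomization takes place on Day 1, after the stop, and the stop applies to every arm. The treatment-emergent tables are unaffected.
- **That the events vanish.** For subjects who reach Day 1, new conditions are recorded and coded, medications from the 30 days before Day 1 go on the CRF (9.2.1), and the Day 1 blood count and vital signs are taken. Screen failures leave a documented reason. Section 12.1 requires CRFs for randomized subjects but does not say that others have none. The loss is from AE and SAE data and from expedited reporting.
- **That an earlier start would capture symptomatic anemia or a transfusion for it.** Section 10.1.1 exempts worsening anemia due to CKD from being an AE at any time. Moving the start alone would leave the most direct effect of the stop uncaptured.
- **That about 3,000 subject-days are at issue (125 × 24).** This puts every subject at the ceiling, and it uses the reading on which epoetin stops at SV2 itself, before eligibility is confirmed.
- **That the sponsor certainly sees nothing.** Section 10.6 refers to a Medical Monitor Plan that is not available here. What can be said is that the protocol text shown obliges no report.

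The version point also stands: Section 10 of the apparently later text cannot be checked.

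None of this supplies a reporting route for a serious event in the gap. The protocol's reason for exempting worsening anemia, that the primary endpoint captures it, also does not carry over: a subject who drops out before Day 1 contributes no endpoint.

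**Conclusion.** The point holds for the protocol version whose Section 10 is visible. Serious events during the required epoetin stop have no expedited reporting route and are not described as harms of conversion. The effect is on the completeness of safety oversight and harm description. The primary endpoint and the between-arm comparison are untouched.

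The size is modest: at least 535 subject-days at planned enrollment, about 2.5% of the reporting-period days, nearly all of it (475) in the Main study. An individual gap can reach about 20 to 24 days, depending on when epoetin is stopped. These figures assume the planned numbers, the minimum stop for every subject and full follow-up to Day 169. No expected number of events can be derived from the documents. Because the repair is cheap, the change is worth making.

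**What to change.** In sections 10.3.1, 9.2.1 and 10.2 and in Appendix A footnote [m], start SAE reporting when epoetin is stopped for the study. From the same time, record AEs attributed to that stop or to another protocol procedure. Say explicitly that this includes subjects who then fail screening, and allow the existing SAE form to be used for them.

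In 10.1.1, state how the worsening-of-anemia exemption applies before the first dose. Without this, serious anemia events or transfusions in the gap would stay uncaptured.

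Present these events in a separate pre-dose listing, which leaves the treatment-emergent tables as they are.

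Check Section 10 of the later protocol version and make the same change there if it has the same start point. The cost is a wording change, slightly more site reporting and one extra listing.
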